## **10. STATISTICS AND DATA ANALYSIS**

#### 10.1 The study diagram

A study diagram has been produced to show participant/patient numbers (estimated) for the study. Please see figure 2.0 below, which should be read in conjunction with the figure in appendix A.

Figure 2.0 Participant numbers - estimates

**a.** Estimated 200 HIV co-infected patients with suspected ATB to be recruited during study arise from the initial overall population of TB suspects presenting at Consortium hospitals. The corresponding study flow diagram for the subgroup would be the same as this study flow diagram, with proportionally smaller numbers. The only difference being that 62% of HIV TB suspects will be recruited and 50% of HIV TB suspects are expected to have a final diagnosis of ATB.

**b.** Proportion of suspects recruited determined by the number of days per week that TB Research Nurses attend participating hospitals – roughly 3 to 4 days at each Unit – enabling a recruitment rate of 34% of TB suspects without ascertainment bias.

c. Exclusion of ATB requires definite alternative diagnosis/absence of TB over 6 months follow-up.

d. Estimates based on average culture positive rates.

e. Estimates based on the study refereed to as Dosenjah et al in Annals of Internal Medicine.

Source: Detailed Project Description (Part II), page 18.

#### **10.2 Sample size calculation**

The primary clinical utility of IGRA results in assessment of suspected active TB is in their negative predictive value, which enables clinicians to reliably rule-out TB from the differential diagnosis. This in turn depends on the diagnostic sensitivity and the prevalence of TB in the tested population. A recent meta-analysis computed diagnostic sensitivity of T-SPOT.TB and QFT-in tube in active TB as 90% and 70% respectively. However, these estimates are based on pooling together several small datasets. The two largest studies to-date (n=194 TB cases diagnosed from n=389 TB suspects; n=216 TB cases diagnosed from n=413 TB suspects) gave more robust estimates of 85.1% (95% CI 79.2, 89.9) and 85.2% (95% CI 76.1, 91.9) for T.SPOT.TB for the respective studies and 78.1% (95% CI 70.7, 84.3) for QuantiFERON-Gold in-tube.

This study has been powered to detect a conservatively estimated 10% difference in diagnostic sensitivity between the tests, assuming a sensitivity of 85% for T-SPOT.TB and 75% for QFT-in tube and skin testing. To detect this difference at the 5% significance level (2-tailed) with 90% power, 855 patients are required (each receiving both tests), assuming a 40% prevalence of active TB in the study population. The number of patients recruited will be 1,012 to allow for missing data, indeterminate results, withdrawal of consent and possible logistical errors. These calculations have been made using methods which account for the paired nature of the data (based on McNemar's test) assuming independence of test errors.

In the HIV-infected subgroup, published evidence indicates that diagnostic sensitivity of QFT-in tube is reduced while that of T-SPOT.TB is unaffected. It is estimated that diagnostic sensitivities will be of 85% and 65% for T.SPOT.TB and QFT-in tube respectively, with this study powered to detect such a difference, at the 5% significance level, assuming a 50% prevalence of active TB in the HIV-infected subgroup; 156 patients are required to give 80% power and we expect to recruit 200 patients.

The previous diagram (figure 2.0) detailed how the numbers of patients in each of the final diagnostic classifications will arise from the initial overall population of patients presenting with suspected TB, in routine clinical practice. Data and all appropriate documentation will be stored for a minimum of 10 years after the completion of the study, including follow-up period, according to Imperial College London policy.

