TB is caused by an active infection with *Mycobacterium tuberculosis* (*M. tuberculosis*). Reliable determination of infection status, whether active or latent, could accelerate diagnostic assessment by enabling rapid exclusion of TB. Current conventional methods of diagnosing active TB primarily rely upon the identification of bacilli through microscopy, nucleic acid amplification and culture which may take several weeks to confirm a diagnosis. While highly specific for *M. tuberculosis* these techniques have poor sensitivity. Clinical symptoms and radiological features indicative of TB, histology (where appropriate) and on occasion the use of the tuberculin skin test (TST) can also be used to determine infection status. However, the sensitivity of TST, which measures the delayed-type hypersensitivity response to intradermal inoculation of a crude mixture of *M. tuberculosis* antigens, is insufficient for reliable exclusion of TB from the differential diagnosis. Poor sensitivity, especially in HIV-infected

patients, often confounded by prior BCG (Bacille Calmette-Guérin) vaccination, can produce false-positive results.

There is an urgent need to develop alternative diagnostic modalities, able to rapidly and reliably exclude the diagnosis of TB; improved diagnosis is essential to contain and reverse the rising global burden of this disease. New blood tests, called interferon gamma release assays (IGRAs) have recently been developed to diagnose *M. tuberculosis* infection. IGRAs detect interferon gamma release from T cells (lymphocytes that play a key role in cell-mediated immunity) in response to *M. tuberculosis*-specific antigens, which are absent from the BCG vaccine and most environmental mycobacteria. Test results are not confounded by previous BCG vaccination, conferring higher specificity than TST. An important component to effective and efficient clinical diagnosis, results are available within 24 hours and do not require the patient to make a return visit. IGRA has been recommended by UK, European and North American guidelines to diagnose latent tuberculosis infection (LTBI) although its role in active TB remains unclear.

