#### 10.3 Data Analysis

Sensitivity, specificity, positive and negative predictive values and likelihood ratios for each test and combination of tests, will be calculated to determine diagnostic accuracy and clinical utility for the representative cohort as a whole and within the appropriate subgroup of HIV co-infected patients. Participants to be included with reference to standard results from categories 1 (culture-confirmed), 2 (highly probable), and 4 (active tuberculosis excluded) for the primary analyses. Categories are described in table 1.0. The proportion of participants in Category 3 (clinically indeterminate) will be reported, and their impact on estimates ascertained by including them in sensitivity analyses. Similarly, sensitivity analyses will be carried out to investigate the impact of including Category 2 participants, particularly regarding test sensitivity. Full disclosure of all results will be reported, including numbers of indeterminate ELISpot and ELISA results.

Comparisons between ELISA and ELISpot IGRA tests will be provided to exploit the paired nature of data, using repeated measures and marginal logistic regression models, utilising the reference standard as an outcome. In the subset of patients presenting with a TST as part of their clinical diagnostic work-up, the performance of this particular test will be compared with IGRA results. Variation in test performance with HIV status and other characteristics will be estimated by including covariates in the models.

The performance of combinations of two or more tests using logistic regression models constructed in the same form as Bayesian updating (post-test odds = pre-test odds x likelihood ratio) by including the log of the pre-test odds of prevalence (a constant term of known value) as an offset in the model, will be assessed. A linear predictor will then estimate log likelihood ratios, rather than log odds ratios. However, bootstrap methods will be required to obtain valid CIs (confidence intervals). Model parameterizations from Knottnerus to compute likelihood ratios for the additional diagnostic value of each test in a testing sequence, will be used. Non-parametric, bias-adjusted CIs for parameter estimates from 1,000 bootstrap samples will be computed.

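### Section 10.2 names skin testing in the contrast powered at 90%, but skin tests exist only for a work-up subset of unstated size, so the 90% is supported for T-SPOT.TB v QFT-in tube only

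*Protocol*

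**What the plan says.** Protocol section 10.2 describes the study as "powered to detect a conservatively estimated 10% difference in diagnostic sensitivity between the tests". The sensitivities behind that difference follow in the same sentence: "assuming a sensitivity of 85% for T-SPOT.TB and 75% for QFT-in tube and skin testing". The error rate and power are set "at the 5% significance level (2-tailed) with 90% power", and the requirement is "855 patients are required (each receiving both tests"). The prevalence used to turn TB cases into patients is 40%. The calculation is paired, based on McNemar's test, with independent test errors. Recruitment is raised to 1,012 to cover missing data, indeterminate results, withdrawn consent and logistical errors. Patients who never have a skin test are not among the listed reasons.

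Sections 7 to 7.3 provide for blood sampling and for both commercial IGRAs on every participant. They list no skin test. Section 10.3 compares TST with the IGRAs only "In the subset of patients presenting with a TST as part of their clinical diagnostic work-up". The background in section 3.2 describes conventional diagnosis as including "on occasion the use of the tuberculin skin test (TST"). The protocol states neither the expected number with a TST nor a power for that subset.

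**The concern.** The 90% depends on every patient in the calculation having both tests of the pair. The study arranges this for T-SPOT.TB and QFT-in tube. It does not arrange it for T-SPOT.TB and TST, although the power sentence names skin testing on the same footing as QFT-in tube. As written, sections 10.2 and 10.3 do not fit together.

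What is at stake is how a T-SPOT.TB v TST result is read. If it shows no difference, a reader of section 10.2 could take it for a negative finding with 90% power, when it may come from far fewer paired TB cases than the calculation assumed.

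**Working it through.** **Inputs from section 10.2.** Two-sided 5% level (z = 1.960); 90% power (z = 1.282); sensitivities 0.85 and 0.75, so d = 0.10; prevalence 0.40; independent test errors.

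**Step 1. Reproduce the plan's figure.**

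- Discordant proportion among TB cases: ψ = 0.85 × 0.25 + 0.15 × 0.75 = 0.2125 + 0.1125 = 0.325.
- TB cases needed: (1.960 + 1.282)² × ψ / d² = 10.507 × 0.325 / 0.01 = 341.5, rounded up to 342.
- Patients needed: 342 / 0.40 = 855, as stated.
- The same formula reproduces the HIV subgroup figure (85% v 65%, 80% power, 50% prevalence): ψ = 0.85 × 0.35 + 0.15 × 0.65 = 0.395; 7.849 × 0.395 / 0.04 = 77.5, rounded up to 78; 78 / 0.50 = 156, as stated.

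The arithmetic is right for two tests done on everyone.

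**Step 2. What 90% would need for T-SPOT.TB v TST.** The same 85% v 75% contrast needs 855 patients with both tests. That is 100% of 855 evaluable patients, or 855 / 1,012 = 84.5% of recruits if nobody is lost for any other reason. For 80% power the formula gives 256 cases, so 256 / 0.40 = 640 patients: 640 / 855 = 75%, or 640 / 1,012 = 63%.

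**Step 3. Power if only a fraction f has a TST.** The protocol gives no f, so the range below is an assumption. The 40% prevalence and the sensitivities of 85% and 75% are taken to hold in the subset.

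Power = Φ(√(n d² / ψ) − 1.960), with n = N × 0.40 × f.

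Example, N = 855 and f = 50%: n = 171; √(171 × 0.01 / 0.325) = 2.294; 2.294 − 1.960 = 0.334; Φ = 0.63.

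| f (assumed) | Paired TB cases, N = 855 | Power | Paired TB cases, N = 1,012 | Power |
|---|---|---|---|---|
| 100% | 342 | 90% | 405 | 94% |
| 84.5% | 289 | 85% | 342 | 90% |
| 75% | 256 | 80% | 304 | 86% |
| 50% | 171 | 63% | 202 | 70% |
| 30% | 103 | 43% | 121 | 49% |
| 20% | 68 | 30% | 81 | 35% |

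The N = 1,012 columns are upper bounds, because the reserve above 855 is meant for other losses. A version of the formula with separate null and alternative variances needs 338 cases (845 patients) and gives powers within one percentage point of those shown.

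**The case against.** The strongest reply is that section 10.2 never attaches 90% to T-SPOT.TB v skin testing in so many words. It speaks of both tests, and the two commercial IGRAs are tests that every participant receives. The HIV paragraph powers only those two, and the primary objectives in section 4.1 do not name TST. On that reading the mention of skin testing is a stray assumption, and section 10.3 already discloses that the TST comparison is confined to a subset.

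This reading is possible, and it limits the point to an inconsistency in a stated power. It does not remove it. The sentence that defines the powered difference includes skin testing. If only the IGRAs were meant, those words do nothing there and still mislead. Section 10.3 does not withdraw them.

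Some stronger inferences should not be drawn:

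- **A known loss of power.** The table depends on assumed fractions. The remark in section 3.2 about occasional use concerns TB diagnosis in general. It is not a testing rate at the participating hospitals.
- **Bias through the clinician's knowledge of the TST.** This is an inference and has no bearing on power. Table 1.0 does not list TST among the reference-standard criteria.
- **A missing comparison of tested with untested patients.** Patients tested in the work-up may differ from the rest, but how to examine this is detail that an analysis plan may hold. Its absence from the protocol is not a fault.

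**Conclusion.** The point holds as a mismatch between sections 10.2 and 10.3. The 90% is supported for T-SPOT.TB v QFT-in tube and is not supported for T-SPOT.TB v TST. Keeping it for TST would require nearly every recruit to be skin tested, which does not fit a comparison described as a subset.

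The size of the shortfall cannot be fixed from the protocol. Across assumed fractions of 75% down to 20%, power runs from about 80% to 30% on 855 patients and from at most about 86% to 35% on 1,012. These figures also assume that the subset shares the planned prevalence and sensitivities.

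A reader might infer that the trial is too small or that 855 is miscalculated. Neither follows: the 855 reproduces exactly, and the sample size and the power of the IGRA head-to-head comparison are unaffected.

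**What to change.** Either of two wording changes resolves it:

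1. Delete *and skin testing* from the power statement in section 10.2. Say that the TST comparison is a subset analysis for which no power is claimed, reported with the number tested and confidence intervals.
2. Keep TST in section 10.2, but state separately the expected number of participants with a TST and the power for that number.

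The cost is a sentence or two of protocol text and one less favourable claim. Recruitment, procedures and the main comparison stay as they are. The second option also needs an estimate of how often TST is used at the participating hospitals.

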#### 10.3 Data Analysis

Sensitivity, specificity, positive and negative predictive values and likelihood ratios for each test and combination of tests, will be calculated to determine diagnostic accuracy and clinical utility for the representative cohort as a whole and within the appropriate subgroup of HIV co-infected patients. Participants to be included with reference to standard results from categories 1 (culture-confirmed), 2 (highly probable), and 4 (active tuberculosis excluded) for the primary analyses. Categories are described in table 1.0. The proportion of participants in Category 3 (clinically indeterminate) will be reported, and their impact on estimates ascertained by including them in sensitivity analyses. Similarly, sensitivity analyses will be carried out to investigate the impact of including Category 2 participants, particularly regarding test sensitivity. Full disclosure of all results will be reported, including numbers of indeterminate ELISpot and ELISA results.

Comparisons between ELISA and ELISpot IGRA tests will be provided to exploit the paired nature of data, using repeated measures and marginal logistic regression models, utilising the reference standard as an outcome. In the subset of patients presenting with a TST as part of their clinical diagnostic work-up, the performance of this particular test will be compared with IGRA results. Variation in test performance with HIV status and other characteristics will be estimated by including covariates in the models.

The performance of combinations of two or more tests using logistic regression models constructed in the same form as Bayesian updating (post-test odds = pre-test odds x likelihood ratio) by including the log of the pre-test odds of prevalence (a constant term of known value) as an offset in the model, will be assessed. A linear predictor will then estimate log likelihood ratios, rather than log odds ratios. However, bootstrap methods will be required to obtain valid CIs (confidence intervals). Model parameterizations from Knottnerus to compute likelihood ratios for the additional diagnostic value of each test in a testing sequence, will be used. Non-parametric, bias-adjusted CIs for parameter estimates from 1,000 bootstrap samples will be computed.

The primary clinical utility of immune-based testing is to exclude TB. Thus, when interpreting analysis and conclusions, focus will be made primarily on sensitivities, negative likelihood ratios and negative predictive values. This analytical plan is similar to that recently developed by [name] and [name].

The magnitude of the interferon-gamma response in both ELISpot and ELISA will be recorded, with cut-off thresholds recommended by the manufacturers of these commercial tests, applied to determine dichotomous positive and negative test results. The continuous data (magnitude of interferon-gamma response) will also be recorded and analysed to characterize the size of response contributes to the diagnostic accuracy of these tests through ROC (Receiver Operating Characteristic) curve analysis. Two co-applicants, [name] and [name], along with others , have previously shown that combining the size of the interferon-gamma ELISpot response with CD4 (Cluster of Differentiation IV) lymphocyte counts (as a ratio of interferon-gamma spot-forming cells to CD4 count) in HIV-infected TB patients can to some extent distinguish active from latent TB. The large study size of the HIV-coinfected TB subgroup (the largest such cohort to date for IGRA evaluation) will enable determination of real clinical utility (or otherwise) of this ratio analysis of IGRA and CD4 counts.

## 11. REGULATORY ISSUES

#### 11.1 Existing (granted) ethics approval – Research Tissue Biobank

Ethical approval has been granted to the Tuberculosis Research Unit for a Research Tissue Biobank by St. Mary's Research Ethics Committee on 14th September 2007 (REC reference: 07/H0712/85) which provides the existing ethical framework for this new study that is to be undertaken. Ethics approval was granted for 5 years and so will cover the duration of this study and a recent inspection in relation to Human Tissue Licence Requirements confirmed that the study procedures, patient confidentiality and governance are all 100% compliant. Newly recruited Research Nurses will have Research Passports to enable them to work across the different Hospitals, using this research system.

#### **11.2 Ethics approval for this study**

This study has received ethical approval from the North West London REC1 ethics committee (REC ref: 11/H0722/8). The research study will be submitted for Site Specific Assessment (SSA) at each participating NHS Trust. The Chief Investigator will require a copy of the R&D approval letter before accepting participants into the study. The study will be conducted in accordance with the recommendations for physicians involved in research on human subjects adopted by the 18th World Medical Assembly, Declaration of Helsinki 1964 and later revisions.

#### 11.3 Consent

Consent to enter the study will be sought from each participant only after a full explanation has been given, an information leaflet offered and time allowed for consideration. Signed participant consent will be obtained. The right of the participant to refuse to participate without giving reasons will be respected. After the participant has been entered on to the study, the clinician remains free to give any treatment that he or she considers might be required, or to refer onto an appropriate healthcare

professional, at any stage if it is felt to be in the participant's best interest; with reasons for doing so, recorded. In such cases the participants will remain within the study for the purposes of follow-up and data analysis. All participants are free to withdraw at any time from the study without giving reasons and without prejudicing further treatment.

#### 11.4 Confidentiality

The Chief Investigator and all members of the research team will preserve the confidentiality of participants taking part in the study and abide by the Data Protection Act. Participants will be allocated a unique indentifying code (anonymised) on recruitment, with no personal identifiers recorded on any samples.

#### 11.5 Indemnity

Imperial College, London as sponsor of this study holds negligent and non-negligent harm insurance policies which apply to this study. These have been arranged through the Joint Research Office.

#### 11.6 Sponsor

Imperial College London will act as the main sponsor for this study. Delegated responsibilities will be assigned to the NHS trusts taking part in this study.

#### 11.7 Funding

Following a successful project grant application, the HTA is funding this study. They are acting as sole funders and this agreement is in place. The investigators will not receive any additional payment above their normal salaries.

#### 11.8 Audits and inspections

The study may be subject to inspection and audit by Imperial College London under their remit as sponsor and other regulatory bodies to ensure adherence to GCP and the NHS Research Governance Framework for Health and Social Care (2nd edition).

#### 12. STUDY MANAGEMENT

#### 12.1 Day-to-day study management

The day-to-day management of the study will be co-ordinated through the trial co-ordinator \*\*\*\*\*tbc\*\*\*\*\*. Close support will be provided by [name] of Imperial College Healthcare.

#### 12.2 Trial steering committee

A Trial Steering Committee (TSC) will be established. This committee will include an independent chair, at least two other independent members and a Patient and Public Involvement representative (recruited through *TB Alert*) along with key members of the co-lead applicants and co-applicants.

#### 12.3 Data monitoring committee

A Data Monitoring Committee (DMC) will also be established. This committee will be independent of the applicants and of the TSC. The group will meet once a year and routinely review data on recruitment, and the prevalence of TB and HIV in the study cohort. The DMC will report to the HTA

programme via the TSC. Recruitment will be monitored by the study co-ordinator every 3 months. If recruitment is unexpectedly low, recruiting HIV-negative patients from a large pool of patients will be begin from Consortium hospitals in which currently only HIV-positive patients are recruited (starting with the St Mary's Hospital site).

## 13. PUBLICATION POLICY

#### 13.1 Dissemination of study findings

The expectation is that after analysis, data from this study will be widely distributed within the medical and scientific community. Facilitated by presentations at local, national and international meetings, findings will be published widely in the medical literature. There is an excellent media department at Imperial College which has considerable experience of publishing high quality research. No identifying participant information will be published.

